#### 5.6.4 Vital Signs

Descriptive statistics for vital signs parameters (diastolic and systolic blood pressure, pulse, respiration rate, temperature, weight) and changes from baseline will be presented by visit and treatment group.

Blood pressure will also be summarized using a shift table from baseline to worst postbaseline by categories defined based on CTCAE grades (Table 5).

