- c: Efforts should be made to conduct study visits on the day scheduled (± 3 days). Clinical laboratory assessments may be conducted anytime within 72 hours prior to the scheduled visit, unless otherwise specified in the Schedule of Procedures/Assessments.
- d: Subjects will be randomized on C1D1 (-1 day) after confirmation of eligibility at the Baseline Visit. All procedures and assessments on C1D1 should be performed after randomization.
- e: See protocol appendices for KPS assessments, NYHA Cardiac Disease Classification, AJCC Staging.
- f: Telephone contact or visit on C1D8 will assess subjects for development of early toxicity. An unscheduled visit can occur prior to C1D15 if deemed necessary by the investigator.
- g: Assessments will include vital signs (resting BP [including date and time of measurement for the first 6 treatment cycles], HR, RR, and body temperature) and BW. Only 1 BP measurement is needed for subjects with systolic BP <140 mmHg and diastolic BP <90 mmHg. If the subject's initial BP measurement is elevated (ie, systolic BP ≥ 140 mmHg or diastolic BP ≥ 90 mmHg), the BP measurement should be repeated at least 5 minutes later. The mean value of 2 measurements at least 5 minutes apart is defined as 1 BP assessment. If the BP assessment (ie, the mean of the 2 BP measurements obtained at least 5 minutes apart) is elevated (ie, systolic BP ≥ 140 mmHg or diastolic BP ≥ 90 mmHg), a confirmatory assessment should be obtained at least 30 minutes later by performing 2 measurements (at least 5 minutes apart) to yield a mean value. Subjects with systolic BP ≥ 160 mmHg or diastolic BP ≥ 100 mmHg must have their BP monitored on Day 15 or more frequently as clinically indicated) until their systolic BP has been ≤ 150 mmHg and diastolic BP has been ≤ 95 mmHg for 2 consecutive treatment cycles. If a repeat event of systolic BP ≥ 160 mmHg or diastolic BP ≥ 100 mmHg occurs, the subject must resume the Day 15 evaluation until systolic BP has been ≤ 150 mmHg and diastolic BP has been ≤ 95 mmHg for 2 consecutive treatment cycles. A diary will be provided to the subject to capture the blood pressure evaluations between study visits. See [Section 9.4.2.1, Management of Hypertension](#), for further details.
 Note: During Cycle 3 and subsequent cycles, subjects may return to the clinic for the Day 15 visit if BP monitoring is required as specified above. The Day 15 visit is mandatory in Cycles 1 and 2.

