- h: Urine dipstick testing for subjects with proteinuria $\geq 2+$ should be performed on Day 15 (or more frequently as clinically indicated) until the results have been 1+ or negative for 2 consecutive treatment cycles). Urine dipstick testing should be performed preferably at the investigational site (but may be performed locally by the primary care physician or a local laboratory if the subject does not have to come for a visit to the site). If a new event of proteinuria $\geq 2+$ occurs, the subject must resume the Day 15 urine dipstick testing for evaluation of proteinuria until results are 1+ or negative for 2 consecutive treatment cycles. For subjects with proteinuria $\geq 2+$, see [Section 9.4.2.2, Management of Proteinuria](#), for further details.
 Note: During Cycle 3 and subsequent cycles, subjects may return to the clinic for the Day 15 visit if urine dipstick testing is required as specified above. The Day 15 visit is mandatory in Cycles 1 and 2.
- i: A comprehensive PE (including a neurological examination) will be performed at the Screening or Baseline Visit, on C1D15, on Day 1 of each subsequent cycle, and at the Off-Treatment Visit. A symptom-directed PE will be performed on C1D1 and at any time during the study as clinically indicated. Height will be measured at the Screening Visit only.
- j: Required if screening PE is performed >7 days prior to C1D1.

Table 7 Schedule of Procedures/Assessments in Study E7080-G000-307: Prerandomization and Randomization Phases

- k: Single 12-lead ECG. Subjects must be in the recumbent position for a period of 5 minutes prior to the ECG.
- l: MUGA scan or echocardiogram will be performed during the Screening Visit and during or within 1 week following the Off-Treatment Visit, or sooner if clinically indicated. Assessment should use the same methodology (MUGA or echocardiogram).

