9.7.1.8.4 VITAL SIGNS

Descriptive statistics for vital signs parameters (ie, systolic and diastolic BP, resting HR, respiratory rate, temperature, and weight) and changes from baseline will be presented by visit and treatment arm. Blood pressure will also be summarized using a shift table by categories defined based on CTCAE Grades. Subjects will be included in the summary if they had both a Baseline value and at least 1 postbaseline value for blood pressure.

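### From Cycle 3, Day 15 vital signs come from subjects selected for high blood pressure or proteinuria, but the by-visit tables do not set those visits apart

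*SAP*

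**What the plan says.** On analysis, SAP Section 5.6.4 names blood pressure, pulse and the other vital signs, then says of the list ending in "respiration rate, temperature, weight) and changes from baseline will be presented by visit and treatment group". Protocol Section 9.7.1.8.4 agrees: "changes from baseline will be presented by visit and treatment arm". Neither limits the visits. SAP Section 8.2.1 only selects one record per subject for each scheduled visit.

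On attendance, the vital-signs row of Protocol Table 7 (Section 9.5.2) is marked on Day 15 in the column running from Cycle 3 to the last cycle. Footnote g then states: "The Day 15 visit is mandatory in Cycles 1 and 2". From Cycle 3, "subjects may return to the clinic for the Day 15 visit if BP monitoring is required as specified above". The trigger is systolic pressure of 160 mm Hg or more or diastolic of 100 or more. Such subjects "must have their BP monitored on Day 15 or more frequently as clinically indicated", until pressure has been at or below 150/95 for two consecutive cycles. Footnote h opens a second route, for dipstick proteinuria of 2+ or more: "subjects may return to the clinic for the Day 15 visit if urine dipstick testing is required as specified above". Table 8 repeats both rules for the Extension Phase in footnotes c and d.

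**The concern.** The same visit label covers two populations. In Cycles 1 and 2, Day 15 is a visit for the whole arm. From Cycle 3 it is called for only in subjects with a recent high blood pressure or proteinuria finding. A table that follows the SAP literally would print both kinds of column in one series.

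Two readings of such a table would mislead. Down the series, a change between a Day 1 and a Day 15 column would mix a change over time with a change in who is measured. Across arms, the later Day 15 columns would compare groups formed by a post-randomization event whose frequency may differ by treatment, so the benefit of randomization is lost there. For blood pressure, part of the selection is on the variable being summarized. The other vital signs and weight are affected too, because they are taken at the same visit.

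**Working it through.** The plan gives no figure to reproduce. The check has two parts.

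**1. Does any rule in the plan separate conditional from universal visits?**

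- Protocol Table 7, vital-signs row: Day 15 is marked in every cycle.
- Footnotes g and h: mandatory in Cycles 1 and 2, conditional afterwards.
- SAP 5.6.4 and Protocol 9.7.1.8.4: summarize by visit, with no exclusion, flag or footnote.
- SAP 8.2.1: removes duplicate records within a visit and does not address conditional visits.
- SAP Sections 9 and 11: dataset specifications and table shells are separate documents, so the columns actually produced cannot be checked.

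No rule was found. The text permits later Day 15 columns and does not require them to be marked.

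**2. Can the size or direction of the distortion be set?**

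Let p_B and p_P be the shares of an arm that ever meet the blood pressure and proteinuria triggers, and o the share meeting both.

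- Attending share: u = p_B + p_P − o
- Share of attendees present through proteinuria alone: s = (p_P − o) / u

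The only guide in the documents is Study 111 (Protocol Section 7.1.4; 30 subjects with RCC): Grade 3 hypertension 3/30 (10%; exact 95% interval 2% to 27%), any-grade hypertension 16/30 (53%), Grade 3 proteinuria 3/30 (10%), any-grade proteinuria 12/30 (40%). As an assumption, these rates stand in for the triggers and are applied to the 350 subjects of Arm B.

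| p_B | p_P | overlap o | u | subjects (u × 350) | s |
|---|---|---|---|---|---|
| 10% | 10% | complete, 10% | 10% | 35 | 0% |
| 10% | 10% | none | 20% | 70 | 50% |
| 10% | 40% | complete, 10% | 40% | 140 | 75% |
| 10% | 40% | none | 50% | 175 | 80% |
| 53% | 40% | complete, 40% | 53% | 187 | 0% |
| 53% | 40% | none | 93% | 327 | 43% |

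For one row in full: 0.10 + 0.40 − 0 = 0.50; 0.50 × 350 = 175; 0.40 / 0.50 = 80%.

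The gap between the column mean and the mean of all subjects in the arm is then

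D = (1 − s) × d_B + s × d_P,

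where d_B and d_P are the gaps for subjects present through the blood pressure route and through proteinuria alone. With s between 0% and 80%, the blood pressure route carries between 100% and 20% of the weight. If proteinuria were unrelated to blood pressure (d_P = 0), D would lie anywhere from 0.2 × d_B to d_B.

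The documents give neither d_B nor d_P, and they do not fix the sign of d_B. Protocol Section 9.4.2.1 starts antihypertensive treatment at a confirmed 140/90, and monitoring continues until readings have stayed at or below 150/95 for two cycles. Some subjects present through the blood pressure route will therefore be treated and controlled when measured.

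**The case against.** The strongest reply is that little depends on these columns. The tables are descriptive, and SAP Section 5.6 includes n, so a fall in numbers at Day 15 would be visible. No test uses these means. Conclusions on hypertension come from outputs without visit columns: the worst-postbaseline shift table, the listing of subjects at or above 140/90, and the adverse event summaries. The shells might also omit these columns. All of this stands, and it keeps the point minor. It does not answer it: a visible drop in n does not tell the reader that the remaining subjects were selected, or on what.

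Three stronger readings are tempting but unsupported.

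- **The later columns show a hypertensive subset.** Footnote h admits subjects with no blood pressure condition, and those admitted for blood pressure may since have been controlled. In the other direction, a dipstick for proteinuria is preferably done at the site "but may be performed locally by the primary care physician or a local laboratory", so some of these subjects may contribute no vital signs and dilute the column less.
- **Later Day 15 columns overstate blood pressure by a definite number of mm Hg.** Any such figure needs blood pressure means, spreads and treatment effects that the documents do not give.
- **Laboratory data are protected and vital signs are not.** The 10% coverage condition in SAP Section 5.6.3 applies to box plots; the laboratory by-visit descriptive tables have no floor either.

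Finally, the footnotes say that subjects may return. They do not bar others from attending on Day 15, but nothing requires it.

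**Conclusion.** The point holds as a cheap improvement of minor severity. Followed as written, the by-visit rule allows Day 15 columns from Cycle 3 that describe subjects selected after randomization for high blood pressure or proteinuria. Those columns do not represent the arm, and they are not comparable with Day 1 columns or between arms. This conclusion needs only the schedule footnotes and the SAP text.

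The size is not established. On Study 111 rates, with Grade 3 hypertension standing in for the blood pressure trigger, about 35 to 175 of 350 Arm B subjects (10% to 50%) would ever qualify, and 0% to 80% of them through proteinuria alone. These are rough illustrations: 30 subjects, adverse event grades instead of the protocol's triggers, one regimen, and ever-rates that ignore discontinuation and the end of monitoring. The direction of the blood pressure distortion is also open.

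Efficacy analyses, Day 1 summaries and adverse event analyses are unaffected. The monitoring rule itself is not in question.

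**What to change.** Add one sentence to SAP Section 5.6.4: by-visit summaries of vital signs use only visits scheduled for all subjects, namely Day 1 of each cycle plus Day 15 of Cycles 1 and 2, and Day 15 readings from Cycle 3 on appear in listings and in the worst-postbaseline shift table. SAP Section 8.2.1 already keeps all observations for worst-value analyses, so nothing is lost there. If the columns are kept, the lesser alternative is to footnote them as conditional visits, with n shown. The same wording should carry into any Extension Phase SAP (SAP Section 5.9), because Table 8 has the same rule.

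The cost is fewer columns in a descriptive safety table. No data collection, sample size or error rate changes.

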**Table 5 Blood Pressure CTCAE Grades**

Grade	Blood Pressure (mm Hg)	
	Systolic	Diastolic
0 (Normal)	$\leq 119$	$\leq 79$
1 (Prehypertension)	120 – 139	80 – 89
2 (Stage 1 Hypertension)	140 - 159	90 – 99
3 (Stage 2 Hypertension)	$\geq 160$	$\geq 100$

For each subject at each visit, SBP and DBP will be graded separately. Then the blood pressure grade will be the worst of the two grades: SBP grade and the DBP grade. The worst blood pressure category per subject during treatment will be used in the shift table.

Subjects with SBP  $\geq 140$  mm Hg or DBP  $\geq 90$  mm Hg on treatment will be listed along with their hypertensive medications.

### 5.6.5 Electrocardiograms

ECG assessments were performed at Day 1 of each cycle. Descriptive statistics for ECG parameters (QTcB [ms] and QTcF [ms]) and changes from baseline will be presented by visit and treatment group.

Shift tables will present changes from baseline in ECG interpretation (categorized as normal; abnormal, not clinically significant; and abnormal, clinically significant) to end of treatment (or end of phase or by visit).

In addition, the number (percentage) of subjects with at least 1 postbaseline abnormal ECG result in QTc Fridericia during the treatment period will be summarized. Clinically abnormal ECG results in QTc Fridericia will be categorized as follows:

Absolute QTc interval prolongation:

QTc interval >450 ms

QTc interval >480 ms

QTc interval >500 ms

Change from baseline in QTc interval:

QTC interval increases from baseline >30 ms

QTC interval increases from baseline >60 ms

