9.7.1.8.5 ELECTROCARDIOGRAMS

Change from baseline to worst postbaseline result in ECG findings (categorized as normal; abnormal, not clinically significant; and abnormal, clinically significant) will be summarized by treatment arm using a shift tables. Descriptive statistics for ECG parameters and changes from baseline will be presented by visit by treatment arm.

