### 5.6.3 Laboratory Values

Laboratory results will be summarized using Système International (SI) units, as appropriate. Laboratory values that are non-missing and reported as ‘below the detectable limit’ of an assay will be replaced by half the detectable limit in the summary tables. On treatment laboratory tests will be defined as laboratory tests conducted from the start of treatment to no more than 30 days after the last dose of study treatment. Central laboratory test results will be primary data source for laboratory analyses. Only when the central laboratory tests results are missing, the local laboratory test results will be used as substitute. Other laboratory parameters collected for some individual subjects will be presented in listing only. Box and Whisker plots will also be generated for individual laboratory parameters and change from baseline by visit for all visits with at least 10% of subjects in all treatment arms.

For all quantitative parameters listed in protocol Section 9.5.1.4 Safety Assessments (Laboratory Measurements), the actual value and the change from baseline to each postbaseline visit and to the end of treatment (defined as the last on-treatment value) will be summarized by visit and treatment group using descriptive statistics. Qualitative parameters listed in protocol Section 9.5.1.4 will be summarized using frequencies (number and percentage of subjects), and changes from baseline to each postbaseline visit and to end of treatment will be reported using shift tables. Percentages will be based on the number of subjects with both nonmissing baseline and relevant postbaseline results.

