### 5.6.6 Other Safety Analyses

Karnofsky Performance Status (KPS) will be summarized by a shift table from baseline to worst postbaseline scale and by frequency counts for each category for each visit.

LVEF (%) obtained by echocardiography will be summarized. The lowest postbaseline value and change from baseline will be summarized with n, mean, SD, median, Q1, Q3, and range. A subject data listing will be provided.

In addition, LVEF quantitative values will be classified into the following 5 categories:

Hyperdynamic = LVEF greater than 70%

Normal = LVEF 50% to 70% (midpoint 60%)

Mild dysfunction = LVEF 40% to 49% (midpoint 45%)

Moderate dysfunction = LVEF 30% to 39% (midpoint 35%)

Severe dysfunction = LVEF less than 30%

A shift table from baseline to the worst postbaseline values will be generated.

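### SAP 5.6.5 drops the protocol's baseline-to-worst-postbaseline ECG shift table, leaves three other endpoints open, and declares no change

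*SAP*

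**What the plan says.** Protocol 9.7.1.8.5 commits to a shift table by arm for "Change from baseline to worst postbaseline result in ECG findings", with three categories: normal, abnormal without clinical significance, and abnormal with clinical significance.

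SAP 5.6.5 uses the same three categories and the same starting point: "Shift tables will present changes from baseline in ECG interpretation". The endpoint of the shift is different: "abnormal, clinically significant) to end of treatment (or end of phase or by visit". Worst postbaseline is not among the options, and the SAP does not say which of the three will be produced.

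SAP Section 7, where departures from planned analyses belong, records none. The SAP's revision highlights for versions 2.0 and 3.0 do not mention 5.6.5 either.

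Two other statements in SAP 5.6.5 bear on the point. ECGs are frequent: "ECG assessments were performed at Day 1 of each cycle". And one ECG measure does get an any-time count: "the number (percentage) of subjects with at least 1 postbaseline abnormal ECG result in QTc Fridericia during the treatment period will be summarized".

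**The concern.** A worst-postbaseline shift and an end-of-treatment shift answer different questions. The first counts subjects who ever had a clinically significant ECG finding after baseline. The second describes their state at the last assessment, when a transient finding may have gone. Protocol 9.7.1 leaves further details to the SAP, but replacing one of these measures with the other changes what is reported.

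At stake is a descriptive safety comparison across two lenvatinib combinations and sunitinib. If the SAP is followed as written, the per-subject ECG table that the protocol promised is not produced, and nothing in the SAP tells the reader so. Because three endpoints are left open, the choice could also be made after the data have been seen.

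**Working it through.** There is no sample size, power or alpha figure to reproduce. The check compares the texts and follows one subject through each table.

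**1. One subject under each design.** Suppose a normal baseline ECG, a clinically significant abnormality at Cycle 4, and a normal ECG at every later assessment, including the last.

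| Table | Where the subject appears |
|---|---|
| Protocol 9.7.1.8.5, worst postbaseline | normal to clinically significant; counted once |
| SAP 5.6.5, end of treatment | normal to normal |
| SAP 5.6.5, end of phase | normal to normal, if resolved by then |
| SAP 5.6.5, by visit | normal to clinically significant at Cycle 4 only; normal to normal at every other visit |

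**2. By-visit counts do not give a per-subject count.** One abnormal count at Cycle 4 and one at Cycle 6 could be one subject seen twice or two subjects. The number ever affected is therefore 1 or 2, and the by-visit table cannot say which.

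**3. How many ECGs lie behind one end-of-treatment value.** The protocol synopsis (Duration of Treatment) estimates about 15 months of treatment. SAP 8.2.2 sets a month at 30.4375 days, and cycles last 21 days:

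15 × 30.4375 / 21 = 456.6 / 21 = 21.7

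That is about 22 Day 1 ECGs per subject, of which an end-of-treatment shift uses one postbaseline value. A by-visit table uses them all. This figure shows how much opportunity there is for a transient finding. It does not measure how many subjects are missed.

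**4. What end of treatment means.** SAP 5.6.5 does not define it. SAP 5.6.3 does so for laboratory data: "to the end of treatment (defined as the last on-treatment value". Whether that definition carries over to ECGs is not stated.

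**5. The SAP's practice elsewhere.** SAP 5.6.4: "Blood pressure will also be summarized using a shift table from baseline to worst postbaseline". SAP 5.6.6, for LVEF: "A shift table from baseline to the worst postbaseline values will be generated". KPS (5.6.6), laboratory CTC grades (5.6.3.1) and dipstick proteinuria (5.6.3.2) also go to worst postbaseline. Qualitative laboratory parameters (5.6.3) do not: their shift tables go to each visit and to end of treatment.

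**6. What other outputs cover.**
- QTcF: any postbaseline value above 450, 480 or 500 ms, or an increase above 30 or 60 ms, is counted per subject (SAP 5.6.5).
- ECG abnormalities that the investigator regards as adverse events are recorded as such (protocol 9.5.1.4.1 and 9.5.1.4.6). If treatment-emergent, they enter the per-subject tables of SAP 5.6.2, and those of 5.6.2.1 if they led to a dose change or discontinuation.
- SAP Section 5 lists every summarized variable by subject, but a listing is not a summary by arm.

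What remains uncovered is a clinically significant finding that is neither a QTcF excursion nor a reported adverse event, such as some rhythm or conduction changes. No planned table counts subjects with such a finding by arm.

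**The case against.** The strongest case on the other side is that little is lost. A finding serious enough to prompt a dose change would normally be reported as an adverse event and counted once per subject, whether or not it resolved. QTc, the one ECG measure given numerical thresholds, is already summarized at any postbaseline time. The by-visit option would show every abnormality at its visit. The SAP's treatment of qualitative laboratory parameters sets a precedent for by-visit and end-of-treatment shifts, so 5.6.5 is not the lone exception. Safety data are summarized descriptively, and no hypothesis test depends on them. Nor is worst postbaseline a neutral benchmark: more ECGs give more chances of an abnormal reading, so it favours arms with shorter treatment.

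Most of this stands, and it limits the point to the residual group identified above. It does not remove the conflict. The protocol planned the ECG shift table in addition to the adverse-event tables, and the SAP drops it without saying so. Apart from the protocol's specific QTc rule, entry into the adverse-event tables depends on the investigator's judgement, which the ECG table was not meant to duplicate.

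A reader might infer that resolved clinically significant abnormalities vanish from the report altogether. The documents do not support that: the by-visit option, the QTcF summary, the adverse-event tables and the listings each retain some or all of them.

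**Conclusion.** The protocol and SAP conflict on the endpoint of the ECG interpretation shift, and the change is undeclared. None of the SAP's three options gives a per-subject worst-postbaseline count by arm. Under two of them, a subject whose abnormality has resolved to normal is shown as normal.

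The consequence is confined to non-QTc findings not reported as adverse events. Its size cannot be derived: neither document gives an incidence of such findings or a rate at which they resolve. A reader might also infer that incidence is understated by some known factor, or understated most in the arm treated longest. Neither follows. The first needs a resolution rate that would have to be invented. The second needs resolution or detection to differ by arm in a known way, and the protocol's 15-month estimate is a single figure for all arms.

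No efficacy result is affected. The point is worth acting on because the correction is small and restores a safety table that the protocol specified.

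**What to change.** In SAP 5.6.5, state that the ECG interpretation shift table runs from baseline to the worst postbaseline result during the treatment period, by arm, as protocol 9.7.1.8.5 requires. Keep the end-of-treatment or by-visit shift as an additional table if wanted, and name which one.

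The cost is one sentence in the SAP and one more summary table, from ECG data already collected. Worst-postbaseline counts rise with the number of ECGs taken, so the table should be read alongside treatment duration in each arm.
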